#### b) Secondary Outcomes

**Aim 1** a) Episodes of symptomatic malaria during study period; b) geometric mean parasite density at delivery; c) Proportion with placental malaria (impression smear, available on a subset); d) Proportion with anemia at delivery (hgb <11 g/dL); e) Proportion with adverse birth outcomes, including preterm delivery (<37 wks), stillbirth, low birth weight (<2500g) or early neonatal death (<7 days); f) Proportion of infants with poor growth at 6 and 12 months of age.

**Aim 2** a) Proportion with anogenital GBS colonization after 35 weeks GA or at delivery; and b) Maternal puerperal and/or neonatal infections prior to hospital discharge c) Proportion with infection with Mycoplasma genitalium (M gen), Trichomonas vaginalis (T vag), and bacterial vaginosis (BV).

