##### b) Participant Inclusion Criteria

- Confirmed HIV-infection (documented in medical record)
- Age  $\geq 16$  years
- Confirmed pregnancy,  $<28$  weeks estimated gestational age (by best obstetric estimate which may include ultrasound or fundal height and LMP)
- Live singleton pregnancy

- Receiving prenatal care at Mboppi Hospital or Mutengene Hospital
- Plan to receive follow up prenatal care and deliver at study facility
- Capable of providing written informed consent
- Able and agree to come to facility for febrile episodes or acute illness during pregnancy (with reimbursement of transportation costs).
- Agree to avoid antimalarial medications outside of study protocol.
- Women receiving standard therapy for HIV infection (any antiretroviral regimen) and standard malaria prophylaxis medications (cotrimoxazole) will be eligible to participate.
- Women with HIV-infection who are not taking antiretrovirals (for any reason) are eligible to participate in the trial if all other study criteria are met.
- Participants will be eligible to participate irrespective of prior or active malaria infection detected at the time of study enrollment.

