### **c) Participant Exclusion Criteria**

- Severe anemia (last hemoglobin <6)
- History of severe adverse reaction to co-trimoxazole or azithromycin
- Active medical problem requiring inpatient evaluation at the time of screening
- Intention of moving far away from the facility during pregnancy or not likely to return for follow up care or delivery
- Signs or symptoms of early or active labor
- Known congenital anomalies
- History of severe cardiac disease (including congestive heart failure, severe valvular disease or arrhythmias).

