## VII. STUDY SCHEDULES AND PROCEDURES

	Screen and Enroll	Follow up Visit (1-6)	Sick Visit (1-9)	Term Visit (1)	Delivery Visit (1)	Postpartum (if no Delivery Visit)	Follow Up Call	Infant Follow Up Call or Visit
Timing of Visit/Call	4-28 weeks	Every 4 weeks	As Needed	35-42 weeks	At Delivery	Within 14 days of delivery 	Within 6 weeks	3, 6, 9, 12 months
FORMS 								
Screening Log (Form 1)	X							
Eligibility (Form 2)	X							
Consent and Randomize (Form 3,4)	X							
Baseline Survey (Form 5)	X							
Follow Up Survey (Form 6)		X		X	X	X		
Med Adherence (Form 7)		X	X	X	X	X		
Sick Call Survey (Form 8)			X					
Outcomes and Labs (Form 9)	X	X	X	X	X	X	X	
Adverse Events (Form 10)		X	X	X	X	X	X	X
Postpartum Phone Call (F 11)							X	
Participant Contact Info (Form 12)	X	X	X	X	X	X	X	
Infant Follow Up (Form 13)								X
CLINICAL AND SAMPLING								
Vitals and Exam	X	X	X	X	X	X		
Venipuncture	X		X	X	X	X		
Finger stick	X	X	X	X	X	X		
Vaginal Swab	X			X	X	X		
Placental biopsy					X			
Directly Observed Therapy	X	X	X	X				
LAB TESTING 								
CBC and differential	X			X	X	X		
CD4 Count				X				
HIV Viral Load					X			
Thick smear	X			X	X	X		
RDT		X	X	X				
DBS for PCR	X	X	X	X	X	X		
Syphilis (RPR/TPHA)	X 			X	X	X		
Xpert GC/CT & GBS NAAT				X	X	X		
SUPPLIES PROVIDED								

Bed Net	X							
Condoms	X	X	X	X				
30 day med supply	X	X	X	X				

 Samples collected at postpartum visit only if they were not collected at prior visits

 Lab testing to be performed on site. Additional testing at UAB is not part of this table.

 In cases of fever or clinical suspicion of malaria.

 RPR testing will be performed for women with a positive treponemal test on enrollment if it has not been done.

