### a) Enrollment Visit

Following the provision of informed consent, study subjects will be randomized to one of two arms. A baseline survey will be administered by study nurses, vital signs will be collected and a brief exam will be performed. The medical chart will be reviewed for additional information. A 30 day supply of medications will be provided by study nurse. Contact information will be collected for the woman and a back-up person (with permission) and women will be given an appointment to return in 30 days. Bed nets, condoms and safe sex counseling will be provided. Partner HIV testing will be recommended, discussed with all women and facilitated, as necessary. Questions will be asked by study staff and entered into a RedCAP database. All forms will be labeled with the unique study ID, visit number and date.

Testing: CBC, thick smear and DBS. RPR confirmatory testing for those with + ANC syphilis screen. Vaginal swab for GC/CT and store. pH. Slides and store.

Treatment: For malaria peripheral parasitemia:

1st trimester – Quinine.

National Guidelines: Three doses of Parenteral Quinine base at 8.3mg/kg x 3 every 8 hours for 24 hours. Each infusion should run for 4 hours. This is relayed by Oral Quinine (tablets) for 3 days if patient can tolerate) and a maximum dose of 1.5 per day of Quinine base. The treatment is for 7 days. If the woman develops contractions on quinine, administer tocolytics.

2nd or 3rd trimester - Artesunate.

Per National Guidelines: Injectable Artesunate IV or IM: 2.4mg/kg at 0, 12, and 24 hours. This is continuous once every 24 hours until the patient can take the oral with ease. This is relayed with Artemether -Lumefantrine for 3 days if she can swallow.

1st dose of study medications will be given under directly observed therapy (DOT).

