## **XII. DATA ANALYSIS AND MANAGEMENT**

Data management and analysis will be led by the University of Alabama at Birmingham under the supervision of the study PI ([name]).

The primary analysis will be by intention to treat for women who are randomized and receive at least 1 dose of study medication.

The “per protocol” analysis will be performed on women who came to at least one follow up visit following the enrollment visit, reported excellent (>90%) medication adherence, and had outcomes captured (ie – not lost to follow up).

**Statistical Analysis:** Descriptive statistics will be used to compare the study participants between each arm and the primary analysis will be intention-to-treat for the primary outcome of proportion of women with parasitemia. The analysis plan for categorical outcomes is chi-square, Fisher’s exact tests as needed for small sample sizes and we plan to use t-test and Wilcoxon Rank-Sum tests for continuous outcomes. Women will be considered lost to follow up if they do not have a study visit after 35 weeks or at delivery for outcome ascertainment.

For the secondary outcomes, the significance of differences in proportion will be explored using the Pearson’s  $\chi^2$  test or Fisher’s exact test. Multivariable regression modeling will be used to evaluate baseline factors associated with parasitemia if there is imbalance between the arms despite randomization. Potential covariates include age, parity, educational level, monthly income, marital status, history of negative birth outcomes, CD4 count, ART adherence, bed net usage, malaria treatment received and number of study visits. All analyses will be performed in SAS v 9.3.

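### The anemia outcome does not separate anemia present at entry from new anemia, and the enrollment hemoglobin enters no stated analysis of it: a minor, avoidable loss of precision

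*Combined protocol and SAP*

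**What the plan says.** **Outcome.** Section III.b, Aim 1 item d) is "Proportion with anemia at delivery (hgb <11 g/dL". Nothing in the definition refers to the woman's hemoglobin at entry. Appendix A lists maternal anemia with the same cut-point.

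**Eligibility.** The only hemoglobin limit is the exclusion in Section V.c: "Severe anemia (last hemoglobin <6". Section V.b sets no hemoglobin level and states: "Participants will be eligible to participate irrespective of prior or active malaria infection detected at the time of study enrollment".

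**Data.** Section VII.a lists for the enrollment visit: "Testing: CBC, thick smear and DBS". The Section VII schedule marks the row "CBC and differential" at enrollment, at the term visit, at delivery and at the postpartum visit. Under Sections VII.e and VII.f, the later tests are done only if the 35–42 week tests were not. A paired entry and late value is therefore planned for women who reach outcome assessment.

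**Analysis.** Section XII: "For the secondary outcomes, the significance of differences in proportion will be explored using the" Pearson chi-square or Fisher's exact test. The only regression is this: "Multivariable regression modeling will be used to evaluate baseline factors associated with parasitemia if there is imbalance between the arms despite randomization". Hemoglobin is not among the potential covariates named for it. T-tests and Wilcoxon tests are provided for continuous outcomes, but Section III defines no continuous hemoglobin outcome.

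**The concern.** A woman who enters at 7 g/dL and ends at 10.5 counts as an event; one who falls from 13 to 11.1 does not. When many women are anemic at entry, the late proportion mixes three things: anemia that persisted, anemia that resolved and anemia that is new. The plan has no analysis that tells them apart. Late hemoglobin is also likely to depend on entry hemoglobin, so leaving that value out adds noise to the comparison of arms.

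Section II names severe maternal anemia among the harms that malaria prevention reduces, so this outcome belongs to the clinical rationale of Aim 1. The trial is sized for parasitemia alone, which is a reason not to discard information on a secondary outcome when the data are already scheduled.

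**Working it through.** **1. The plan's own figure.** Section XI gives 134 per arm for parasitemia of 30% against 15%, with 80% power and two-sided 0.05. It gives no rate, effect or power for anemia.

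- Uncorrected: n = [1.96·√(2·0.225·0.775) + 0.8416·√(0.30·0.70 + 0.15·0.85)]² / 0.15² = 120.5, so 121.
- With continuity correction: (120.5/4)·[1 + √(1 + 4/(120.5·0.15))]² = 133.5, so 134, as stated.
- Recruitment: 134 × 1.15 = 154.1, so 154. After 15% loss, 154 × 0.85 = 130.9, so 131 per arm is used from step 3 on.

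**2. Does anemia at entry necessarily dilute the contrast?** Let b be the share anemic at entry, q the share of them still anemic at the end on control, and e the proportional reduction of q by the drug. New anemia in the other women is set at 30% against 15%, borrowed from Section XI for illustration only. Then p(control) = b·q + (1−b)·0.30 and p(drug) = b·q·(1−e) + (1−b)·0.15. With 134 per arm:

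| Share anemic at entry (assumed) | Nobody recovers (q=1, e=0): difference, power | Drug also resolves anemia (q=0.7, e=0.5): difference, power |
|---|---|---|
| 0% | 15.0 points, 84% | 15.0 points, 84% |
| 30% | 10.5 points, 41% | 21 points, 96% |
| 50% | 7.5 points, 24% | 25 points, 99% |
| 70% | 4.5 points, 14% | 29 points, >99% |

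Dilution can be severe or absent. It depends on whether entry anemia responds to the drug, and only results shown by entry status would reveal that.

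**3. What the analysis choice costs.** Assumed, because the documents give none of these: late hemoglobin on control with mean 10.8 and SD 1.3 g/dL, true gain 0.4 g/dL, correlation r between entry and late values of 0.3 to 0.6.

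- Proportions below 11: Φ(0.2/1.3) = 0.561 against Φ(−0.2/1.3) = 0.439, difference 0.122. Standard error √(2·0.5·0.5/131) = 0.0618. Power ≈ Φ(0.122/0.0618 − 1.96) ≈ 51%.
- Unadjusted t-test: 0.4/(1.3·√(2/131)) = 2.49. Power ≈ Φ(0.53) ≈ 70%.
- ANCOVA: 2.49/√(1−r²) = 2.61 at r=0.3 and 3.11 at r=0.6. Power ≈ 74% and 88%.

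Simulation of the same setting, which also covers adjusted logistic regression, agrees within simulation error:

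| Analysis | r=0.3 | r=0.6 |
|---|---|---|
| Chi-square on <11 g/dL (planned) | 52% | 53% |
| Logistic on <11 g/dL, adjusted for enrollment hemoglobin | 53% | 60% |
| Unadjusted t-test on hemoglobin | 68% | 72% |
| ANCOVA on hemoglobin | 72% | 86% |

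**4. Where the gain comes from.** At r=0.3, ANCOVA gains 72 − 52 = 20 points, of which 68 − 52 = 16 come from dropping the cut-point and 4 from the enrollment value. At r=0.6 it gains 86 − 53 = 33 points, of which 72 − 53 = 19 come from the cut-point and 14 from the enrollment value.

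**5. Validity.** With no true effect, simulated type I error was about 4–6% for chi-square, adjusted logistic and ANCOVA (134 per arm, mean 11.0, SD 1.3).

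**6. A smaller effect.** At a gain of 0.2 g/dL, chi-square has about 17% power and ANCOVA about 26–33%.

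**The case against.** **The comparison is already valid.** Allocation is randomized and stratified by site, so entry anemia is balanced in expectation and the test allows for chance imbalance. This stands. A reader might infer that the planned result is biased and that enrollment hemoglobin would correct it. The documents do not support that: the issue is precision.

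**Women anemic at entry are not fixed events.** A reader might also infer that every such woman counts as an event whatever the drug does. She counts only if she is still below 11 g/dL at the end. Section VII.a treats malaria found at enrollment, entry is before 28 weeks, and resolution of anemia can itself be a drug effect. Step 2 shows that dilution is not automatic.

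**The cut-point is a legitimate choice.** Anemia status at delivery is a clinical outcome, and any threshold treats values on either side of it this way. Most of the power gain at low correlation comes from abandoning the threshold, so it should not be credited to the unused enrollment value. This stands. It argues for adding a continuous outcome, not for replacing the stated one.

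**The inputs are assumed.** If hemoglobin benefit came only through the planned 15-point fall in parasitemia, a mean gain of 0.4 g/dL would need 0.4/0.15 ≈ 2.7 g/dL per woman spared; repeated infections or other pathways would lower that. Enrollment falls anywhere from 4 to 28 weeks, so the correlation is unknown and could be below 0.3. This stands as a limit on the size.

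**The covariate list proves little.** It serves a parasitemia model, is labelled as potential, and the generic baseline comparison could include hemoglobin. That is fair, but neither brings the enrollment value into the anemia comparison, so the gap remains.

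**Conclusion.** The point holds as a matter of precision. The anemia outcome pools anemia present at entry with new anemia, and a baseline value that is already scheduled is used in no stated analysis of it. The unadjusted comparison keeps its type I error and needs no correction.

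For the stated binary outcome, adjustment gains little when entry and late hemoglobin are weakly correlated (about 1 point at r=0.3) and about 7 points at r=0.6. A continuous companion outcome gains more, about 20 to 33 points over the planned test at an assumed gain of 0.4 g/dL. At 0.2 g/dL no analysis would be likely to detect the effect. All hemoglobin inputs, and the share of women anemic at entry, are assumptions.

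The effect on the trial is minor. This is one of six Aim 1 secondary outcomes in a Phase II test of concept. The plan says only that for such outcomes "the significance of differences in proportion will be explored", and it claims no power for anemia. No primary conclusion or sample size depends on it.

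**What to change.** Keep the proportion below 11 g/dL as the stated secondary outcome, and add to Sections III.b and XII, before unblinding:

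- Analyze that proportion by logistic regression adjusted for enrollment hemoglobin (continuous) and site.
- Show it separately for women below 11 g/dL and at or above 11 g/dL at enrollment.
- Add late-pregnancy or delivery hemoglobin as a continuous companion outcome, analyzed by ANCOVA with enrollment hemoglobin and site as covariates.
- Name the enrollment blood count as the covariate, because eligibility rests on the last recorded value, which may be a different measurement. State which late blood count is used when more than one exists.

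The cost is a few sentences of analysis text, with no new visits, samples or participants. If added after unblinding, these analyses would be post hoc.

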**h) Follow Up Phone Call or Visit for Infant Outcomes – Every 3 months until 1 year**

Women will be contacted by phone every three months to ask how the baby is growing. Information from medical visits about the baby's height and weight will be asked as well as any information about infant hospitalizations or sick clinic visits or death. Women will be encouraged to bring the baby to the clinic for a visit at 6 months and 12 months to measure height, weight and head circumference.

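### Infant growth is analysed only as an undefined poor-growth proportion at 6 and 12 months, although height and weight are planned to be measured at those ages

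*Combined protocol and SAP*

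**What the plan says.** Section III.b lists infant growth once, as Aim 1 f): "Proportion of infants with poor growth at 6 and 12 months of age". Neighbouring items carry thresholds (haemoglobin below 11 g/dL, birth weight below 2500 g, delivery before 37 weeks). This one has no measure, reference standard or cut-off, and none is given elsewhere.

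The schedule table in Section VII puts infant contacts at 3, 6, 9 and 12 months. Section VII.h separates two kinds of data:

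- Quarterly contact is by telephone: "Women will be contacted by phone every three months to ask how the baby is growing". At these calls, information from medical visits on "height and weight will be asked as well as any information about infant hospitalizations or sick clinic visits or death".
- Study measurement is planned at two ages only, where mothers are encouraged to "bring the baby to the clinic for a visit at 6 months and 12 months to measure height, weight and head circumference".

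For analysis, Section XII states "For the secondary outcomes, the significance of differences in proportion will be explored" with Pearson's chi-square or Fisher's exact test. It also says "we plan to use t-test and Wilcoxon Rank-Sum tests for continuous outcomes", but no continuous infant growth outcome is listed for that sentence to apply to. No repeated-measures model is described. Section XIV.b makes infant follow-up optional in the consent.

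**The concern.** Weight and length are continuous, and the same infant may be measured at both ages. The plan reduces each measurement to yes or no and implies a separate comparison at each age. Two infants just either side of the cut-off count as opposites, while two infants far apart on the same side count as equal. An infant seen at only one age contributes nothing to the other comparison.

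With measure, standard and cut-off all open, the definition could also be chosen after the data are seen. What is at stake is how much the trial can say about infant growth, with an infant sample that may be smaller than the maternal one because follow-up is optional.

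**Working it through.** **The plan's own figure.** There is no sample size, power or prevalence for infant growth. The nearest figure is Section XI's 134 evaluable women per arm (30% against 15%, 80% power, two-sided 0.05). With mean proportion 0.225 and difference 0.15:

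- n = [1.96·√(2·0.225·0.775) + 0.8416·√(0.21 + 0.1275)]² / 0.15² = (1.1575 + 0.4889)² / 0.0225 = 120.5, so 121.
- With continuity correction: (120.5/4)·[1 + √(1 + 4/(120.5·0.15))]² = 133.5, so 134.

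The figure reproduces. It is used below as an optimistic number of infants per arm.

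**Loss at one age.** Let p be the share of infants flagged. The documents do not give p, so it is an assumption. For a normal outcome with the same shift for all infants, the yes/no comparison keeps φ(z)² / [p(1 − p)] of the information in the comparison of means, where φ(z) is the standard normal density at the cut-off.

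| p | φ(z) | kept | lost |
|---|---|---|---|
| 10% | 0.1755 | 0.0308/0.0900 = 0.34 | 66% |
| 15% | 0.2332 | 0.0544/0.1275 = 0.43 | 57% |
| 20% | 0.2800 | 0.0784/0.1600 = 0.49 | 51% |
| 25% | 0.3178 | 0.1010/0.1875 = 0.54 | 46% |
| 30% | 0.3477 | 0.1209/0.2100 = 0.58 | 42% |
| 50% | 0.3989 | 0.1592/0.2500 = 0.64 | 36% |

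The last row is the best case, so the loss at one age is never below 36%. It reaches one half when p is about 21% or lower.

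**Both ages pooled.** The plan does not say that the two ages would be combined. If they were, the fair comparison is two yes/no ages against two continuous ages. With correlation ρ between ages of 0.5, 0.7 and 0.9 (assumed), the share kept is 0.411, 0.413 and 0.393 at p = 10%, and 0.655, 0.662 and 0.642 at p = 30%. The loss is then 59–61% and 34–36%.

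**Contribution of months 3 and 9.** The variance of a mean over k equally correlated ages is proportional to [1 + (k − 1)ρ]/k. Four ages against two:

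- ρ = 0.5: 0.625/0.75 = 0.833, a 17% reduction.
- ρ = 0.9: 0.925/0.95 = 0.974, a 3% reduction.

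This treats reported values as being as good as measured ones, so it flatters the extra ages.

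**What this means for power.** Take 134 infants per arm and a shift of 0.35 SD (an illustration, not a figure from the plan).

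- Continuous, one age: 0.35·√(134/2) − 1.96 = 0.905, power 82%.
- Continuous, two ages, ρ = 0.7: 2.865/√0.85 − 1.96 = 1.147, power 87%.
- Continuous, four ages, ρ = 0.7: 2.865/√0.775 − 1.96 = 1.294, power 90%.
- Yes/no, one age: 10% against 5.1% gives 32%; 20% against 11.7% gives 46%; 30% against 19.1% gives 55%.

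**The case against.** The endpoint ages coincide with the two ages at which the study itself plans to measure. Restricting the outcome to them is defensible, because months 3 and 9 rest on what is asked by telephone about outside visits. A reader might infer that a large part of the loss comes from ignoring those two ages; the 3–17% above shows that it does not.

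A reader might also infer that the plan throws away half or more of the information. The documents do not support that as a flat statement, because the share flagged is unknown and at 25% or 30% the loss is below half. The values are collected and remain available, so the loss lies in the stated analysis.

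Nor do the documents say that clinic measurements and telephone reports are mixed in the 6- and 12-month outcome. They leave the source unspecified.

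Two further points stand. The formula assumes a uniform shift; if azithromycin acted mainly on the smallest infants, these losses would not apply, which is a reason to keep the proportion as a summary. And the outcome is secondary, described as exploratory, carries no power claim and does not appear in the Appendix A design summary. Infant follow-up also serves other purposes, since hospitalisations, sick visits and deaths are collected.

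None of this supplies the missing definition or a continuous growth outcome.

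**Conclusion.** The point holds in limited form. As written, the plan compares an undefined proportion at each of two ages where continuous measurements are planned. At one age this loses about 42–66% of the information if 30–10% of infants are flagged, and at least 36% at any cut-off. These sizes rest on a normal outcome, a uniform shift and an assumed share flagged. The cut-off causes most of the loss; the omission of months 3 and 9 causes little. The missing measure, standard and cut-off can be read directly from the document and need no assumption. The consequence is a weaker and less well-defined secondary comparison, with no effect on the primary aims.

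**What to change.** Before unblinding, amend Sections III.b and XII as follows.

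- **Outcome:** age- and sex-standardised weight-for-age and length-for-age z-scores at 6 and 12 months. Name the growth standard and state how age is handled for infants born preterm.
- **Analysis:** a linear mixed model with arm, age, arm by age and site, and a random infant effect, so that infants measured at only one age are kept.
- **Data source:** clinic-measured or record-documented values in the main analysis; mother-reported values and the 3- and 9-month values in a sensitivity analysis.
- **Proportion:** keep it as a descriptive summary, below a z-score cut-off stated in advance.
- **Data capture:** make sure that infant sex and the date and source of each measurement are recorded. Section VII lists Form 13 by name only, so some of these may already be there.

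The cost is plan wording and possibly a few form fields, with no extra visit. The downside is that a z-score difference is slightly harder to explain than a proportion.
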